### ***Number of patients with special event per 100 patient-years***

The number of patients with at least one specific event per 100 patient-years will be calculated as the number of patients having a specific event in question divided by the total person-year among patients at risk of an initial occurrence of the specific event in question. In particular, it is computed as follows:

$$100 \times \frac{n}{\sum t_i}$$

Where n is the number of patients with the specific events;  $t_i$  is patient exposure time in person-year unit. For each of the specific events of interest, the exposure time for patients who have experienced the specific events will be defined as the time to first specific event in question, whereas the exposure time for those who have not had this specific event will be total duration of exposure as defined above. Please note, the time to first PCSA will be calculated using the midpoint of the time interval between the first assessment showing the PCSA and the previous assessment.

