#### **2.4.4 Analyses of safety data**

##### ***General common rules***

All safety analyses will be performed on the safety population as defined in [Section 2.3.2](#), unless otherwise specified, using the following common rules:

- The baseline value for safety parameters is the original baseline from the previous studies.
- The value at Week 0 is the last non~ missing measurement in data collected at scheduled visits: visit1, visit2 and/or visit1/2 in LTS11210 or EOT visit of previous studies prior to first IMP in LTS11210 study design.
- The Potentially Clinically Significant Abnormality (PCSA) values are defined as abnormal values considered medically important by the sponsor according to predefined criteria/thresholds based on literature review and defined by the sponsor for clinical laboratory tests, vital signs and ECG (PCSA version in BTD-009536 version 3, see [Appendix A](#)).
- PCSA criteria will determine which patients had at least one PCSA during the TEAE period, taking into account all evaluations performed during the TEAE period, including non-scheduled or repeated evaluations. The number of all such patients will be the numerator for the on-treatment PCSA percentage.
- The treatment emergent PCSA denominator by group for a given parameter will be based on the number of patients assessed for that given parameter in the TEAE period by treatment received on the safety population.
- For quantitative safety parameters based on central laboratory/reading measurements, descriptive statistics will be used to summarize results and change from baseline values by visit and treatment received. Summaries will include the endpoint value. The endpoint value is commonly defined as the value collected at the same day/time of the last dose of investigational product. If this value is missing, this endpoint value will be the closest one prior to the last dose intake.
- The analysis of the safety variables will be essentially descriptive and no systematic testing is planned.

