### ***Number of TEAE per 100 patient years***

The number of TEAE per 100 patient years is defined as the total number of TEAEs divided by the total exposure (expressed under the unit of 100 patient years) of the corresponding treatment group. Specifically, it is calculated as follows for each treatment group:

$$\text{Number of TEAE/100 patient years} = (\text{Total number of TEAEs}) / \text{total treatment duration (Unit: 100 patient years)}$$

The total treatment duration is defined as [(end of TEAE period) – (date of first IMP) + 1], where the end of TEAE period is defined as minimum [(the last IMP + 60 days), (last contact date), (death date)], where the last contact date is defined as maximum [last complete AE start date, last visit date, last subject vital status date].

The number of PCSA per 100 patient years for the laboratory values, vital signs and ECGs will be defined similarly.

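### PCSA rates per 100 patient-years mix abnormalities already present on entering LTS11210 with new ones, because no rule removes patients who meet the criterion at Week 0

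*SAP*

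**What the plan says.** Five rules in the SAP act together here.

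- Numerator (2.4.4, General common rules): "PCSA criteria will determine which patients had at least one PCSA during the TEAE period". All evaluations in that period count, including unscheduled ones.
- Baseline (same section): "The baseline value for safety parameters is the original baseline from the previous studies". SAP 2.4.4.3 stratifies laboratory PCSAs by status at that original baseline. A Week 0 value is also defined in 2.4.4, but no PCSA rule uses it.
- Start of person-time (2.1.3, Observation period): the treatment epoch begins at the first LTS11210 dose. In 2.5.1, "The total treatment duration is defined as [(end of TEAE period) – (date of first IMP) + 1".
- Event-count rate (2.5.1): "The number of PCSA per 100 patient years for the laboratory values, vital signs and ECGs will be defined similarly".
- Patients-with-event rate (2.5.1): the number of patients with the event is "divided by the total person-year among patients at risk of an initial occurrence of the specific event in question". The next sentences give every patient a time: "the exposure time for patients who have experienced the specific events will be defined as the time to first specific event in question", and full exposure for everyone else. For PCSAs, "the time to first PCSA will be calculated using the midpoint of the time interval between the first assessment showing the PCSA" and the preceding one.

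Adverse events are treated differently. SAP 2.1.3.1 classes events still ongoing from the parent study as pre-treatment.

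**The concern.** Consider a patient who was normal at the parent-study baseline, became abnormal during the parent study, and is still abnormal at Week 0 and at the first LTS11210 test. Under the written rules this is a first PCSA in the normal/missing stratum, with days to weeks of person-time. The onset belongs to the parent study, whose person-time is left out.

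Such patients are likely to exist. Protocol 4.1.2 reports lower neutrophils and raised ALT and LDL on sarilumab in EFC11072 Part B. Exclusion E 14 in Protocol 7.3 keeps out only patients who meet permanent-discontinuation criteria, such as neutrophils below 500/mm3 or ALT above 5 times ULN (Protocol 11.2.1). The PCSA thresholds in SAP Appendix A are much milder, for example neutrophils below 1.5 Giga/L in non-Black patients and LDL of 4.1 mmol/L or more.

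A reader of the report would take a rate per 100 patient-years as the rate at which abnormalities arise during long-term treatment. It would instead combine entry prevalence with new onset, in proportions that differ between the previous-treatment groups that SAP 2.3.1 wants to look across.

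**Working it through.** The plan states no PCSA rate, so there is no figure to reproduce. The check applies the patients-with-event formula of SAP 2.5.1, 100 × n / Σt, to a simple model.

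**Inputs from the documents**
- Follow-up T: 264 weeks (SAP 1.1) = 264 × 7 / 365.25 = 5.06 years.
- Time credited to a patient already abnormal at entry, t0: the midpoint from Day 1 to the first post-dose test. That is 7 days for haematology and liver tests (Day 15), 14 for lipids (Day 29), 28 for chemistry (Day 57) and 168 for ECG (Day 337).

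**Assumed, because the documents do not give them**
- p, the proportion meeting the criterion at Week 0: 1% to 20%.
- L, a constant true new-onset rate among the rest: 1, 5 or 10 per 100 patient-years.
- Every patient abnormal at entry is abnormal again at the first post-dose test, and all patients are followed for T.

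**Formula**

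Reported rate = 100 × [p + (1−p)(1−e^(−LT))] / [p·t0 + (1−p)(1−e^(−LT))/L]

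**Worked case**: 1000 patients, p = 10%, L = 0.05 per year, haematology.
- 1 − e^(−0.05 × 5.06) = 0.2235, so new events = 900 × 0.2235 = 201.2.
- Person-years of patients free at entry = 201.2 / 0.05 ≈ 4023.3 (unrounded inputs).
- Person-years of the 100 already abnormal = 100 × 7 / 365.25 = 1.9.
- SAP rule: 100 × (100 + 201.2) / (1.9 + 4023.3) = 7.48.
- Without the 100 patients abnormal at Week 0: 100 × 201.2 / 4023.3 = 5.00.

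**Reported rate per 100 patient-years, T = 264 weeks, haematology**

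| True rate | p = 1% | p = 5% | p = 10% | p = 20% |
|---|---|---|---|---|
| 1 | 1.20 | 2.07 | 3.25 | 6.06 |
| 5 | 5.23 | 6.18 | 7.48 | 10.58 |
| 10 | 10.25 | 11.32 | 12.79 | 16.28 |

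With one year of follow-up, a true rate of 5 and p = 10%, the reported rate is 16.36, so shorter follow-up makes the overstatement larger.

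**Does the midpoint rule drive it?** No. At a true rate of 5 and p = 10%, the four values of t0 give 7.48, 7.48, 7.47 and 7.40. The cause is the missing Week 0 exclusion.

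**Is there a fixed direction between groups?** The table shows the reported rate at a true rate of 5 for four assumed patterns of entry prevalence, by weeks of parent-study sarilumab.

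| Assumed entry prevalence | 0 | 2 | 12 | 24 | 52 |
|---|---|---|---|---|---|
| Rises linearly to 8% at 52 weeks | 5.00 | 5.07 | 5.42 | 5.86 | 6.94 |
| Reaches 8% by Week 4, then flat | 5.00 | 5.93 | 6.94 | 6.94 | 6.94 |
| 10% at Week 2, falling to 3% | 5.00 | 7.48 | 7.10 | 6.66 | 5.69 |
| 40% if unexposed, 5% if exposed (CRP-like) | 19.86 | 6.18 | 6.18 | 6.18 | 6.18 |

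The ordering follows entry prevalence, not length of exposure. The event-count rate was not sized. It has the same start of person-time and the same lack of a Week 0 rule, so it mixes the two kinds of event as well.

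**The case against.** The at-risk wording in SAP 2.5.1 can be read as meant to exclude patients already abnormal at entry. That reading is fair as to intent, but the sentences that follow assign time to patients with and without the event and remove nobody. The midpoint rule does not settle it either. If Week 0 is taken as the first assessment showing the PCSA, onset falls before person-time starts. If it is not, an old abnormality is dated as new.

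The parent-study baseline is a deliberate and consistent choice, and the n (%) tables built on it give a legitimate cumulative picture. That stands, and those tables should stay.

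The stakes are limited. SAP 2.4.4.3 to 2.4.4.5 list PCSA incidence and descriptive summaries. The rates appear only as conventions in 2.5.1, and "The analysis of the safety variables will be essentially descriptive and no systematic testing is planned". The primary endpoint is adverse events (SAP 2.1.3), and carried-over adverse events are already set aside. This also stands. The sizes above rest on assumed prevalence: at 1% and a true rate of 5, the excess is only 5%.

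Three stronger readings are tempting, and the documents do not support them.

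- A reader might infer that inflation is greatest where parent-study sarilumab exposure was longest. Tocilizumab patients had no parent-study sarilumab but can carry lipid PCSAs in (Protocol 10.2.10). CRP is a PCSA (Appendix A) and is expected to fall sharply on the drug (SAP 2.1.4), so CRP carry-over should be commonest in former placebo patients. Entry exclusions can also lower prevalence after longer exposure.
- A reader might infer that former placebo patients carry nothing in. Some EFC11072 Part B patients received open-label sarilumab rescue before rolling over (SAP 1.1), and changes in weight or creatinine from the original baseline can occur on placebo.
- A reader might infer that the study's primary question is compromised. It is not, because the primary endpoint is the incidence of adverse events.

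**Conclusion.** The gap is real. Followed as written, SAP 2.5.1 reports PCSA rates above the new-onset rate whenever some patients enter with the abnormality and show it again after the first dose. The Week 0 value is pre-dose and is not itself counted, so persistence or recurrence is needed.

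Under the stated assumptions (constant hazard, full 264-week follow-up, all entry abnormalities persisting), a true rate of 5 per 100 patient-years is overstated by 5%, 24%, 50% and 112% at 1%, 5%, 10% and 20% entry prevalence. The relative excess is larger for rarer abnormalities. These figures are illustrations, not estimates for this trial.

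The amount varies by parameter and previous treatment, and no direction between groups can be stated in advance. The point should be corrected before the final analysis, as an improvement to supporting safety output.

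**What to change.** Add the following to SAP 2.5.1, for both PCSA rates and for time to first PCSA:

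- Calculate them only among safety-population patients whose Week 0 value, as already defined in 2.4.4, does not meet that criterion.
- For criteria defined by change from baseline, judge Week 0 status against the original baseline.
- Report separately the number of patients who meet the criterion at Week 0.
- State how a missing Week 0 value is classed.
- Keep the n (%) tables by original baseline status as the cumulative view.

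The cost is a short SAP insertion and one derived Week 0 flag per criterion, from data already collected. The downside is a slightly smaller at-risk set and one extra table column.

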## 2.5.2 Data handling conventions for efficacy variables

The missing data handling rules are summarized in a table in [Appendix C](#).

### *ACR20/ACR50/ACR70*

In the primary method of missing data handling, the data collected after treatment discontinuation will be set to missing. No imputation of missing post-baseline values will be performed. Responder status will be determined if possible. With these rules patients will automatically become non-responders for all time points beyond the time point they discontinue study treatment.

Patients with insufficient data (ie, TJC, SJC, and at least 3 of the remaining 5 ACR components) at baseline and a time point will be non-responders in ACR20/ACR50/ACR70 at that time point.

### *ACR components - TJC/SJC*

When calculating the TJC and SJC, with individual missing joint scores (the “replaced or fused” joints are not taken into consideration for the swelling or tenderness) imputed as the mean of the scored joints, the TJC/SJC after imputation are as follows:

$$TJC/SJC = \text{sum (scored tender/swollen joints)} * (\text{number of joints in the full joint set} / \text{number of scored tender/swollen joints})$$

The number of joints in the full joint set is defined as (68 – number of replaced or fused joints) for tenderness; (66 – number of replaced or fused joints) for swollenness; and the scored joints refer to those with an answer (0 – no pain, 1- pain).

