## 8.9 CONCOMITANT TREATMENT

A concomitant treatment is any treatment received by the patient, at the same time as the IMP(s), other than medications. Treatments received during the study should be recorded on the corresponding pages of the patient's e-CRF as appropriate.

Joint replacement is permitted during the study. The IMP should be temporarily interrupted prior to surgery as per applicable guidelines and the IMP restarted as soon as proper wound healing is established.

NOTE: The IMP can be temporarily discontinued for  $\leq 59$  days (3 IMP doses can be missed). If the re-initiation of the IMP occurs later than 38 days since the last IMP dose (2 IMP doses were already missed), the IMP has to be administered at the study site and the patient to be observed for 30 minutes for any medical events.

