#### **2.1.4 Efficacy endpoints**

Efficacy is a secondary endpoint of this study. The efficacy variables will include:

- ACR20 response over time up to Week 264
- ACR50 and ACR70 response over time up to Week 264
- Change from baseline in ACR components up to Week 264
- DAS28 –CRP response over time

- DAS28 remission over time
- EULAR response over time
- Change from baseline in the van der Heijde modified total Sharp score (for patients from EFC11072 Part B Cohort 2 and Cohort 1 selected dose arms with an end of treatment X-ray evaluation) at Weeks 48, 96, 144 and 192 or EOT if EOT is prior to Week 192
- Incidence of radiographic progression of the van der Heijde modified total sharp score at Weeks 48, 96, 144, and 192 or EOT if EOT is prior to Week 192
- Change from baseline in HAQ-DI over time up to Week 264.

Note that TJC and SJC (both based on 28 joints), patient's global assessment of disease activity and hs-CRP will still be assessed after Week 264 to calculate DAS28.

As mentioned before, the baseline value for efficacy parameters is the original baseline from the previous study databases for patients who rolled over to LTS11210.

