#### **A) ACR20 response over time**

To be classified as an ACR20 Responder, a patient must achieve 20% improvement in the Tender joint count (68 joints) and the Swollen joint count (66 joints), as well as 20% improvement in at least 3 of the following 5 assessments:

- Levels of an acute phase reactant (CRP level)
- Patient's assessment of pain based on the 0 – 100mm Visual Analogue Scale (VAS)
- Patient's global assessment of disease activity based on the VAS
- Physician's global assessment of disease activity based on the VAS
- Patient's assessment of physical function based on the HAQ\_DI

The 7 ACR components assessing the signs and symptoms of RA are measured as follows

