##### a) Tender Joint Count (TJC)

A total of 68 joints will be assessed for tenderness. The 68 joints to be examined for tenderness are: temporomandibular (n=2), sternoclavicular (n=2), acromioclavicular (n=2), shoulder (n=2), elbow (n=2), wrist (n=2), metacarpophalangeal (n=10), interphalangeal of thumb (n=2), distal interphalangeal (n=8), proximal interphalangeal (n=8), hip (n=2), knee (n=2), ankle mortise (n=2), ankle tarsus (n=2), metatarsophalangeal (n=10), interphalangeal of great toe (n=2), and proximal/distal interphalangeal of the toes (n=8).

A formal count of the joints will be performed by a trained independent assessor. Joint tenderness is defined as pain induced by the pressure of the joints, exerted by the assessor's thumb and index finger. The assessor will classify each joint as painful yes/no and swollen yes/no. A score of 0/1 will be given to each tender joint with 0 representing no pain and 1 representing pain. The tender joint count ranges from 0 to 68 where 0 is considered the best and 68 the worst.

b) Swollen Joint Count (SJC)

The 66 joints to be examined for swelling are the same as those examined for tenderness, except the hip joints are not included.

A formal count of the joints will be performed by a trained independent assessor. The assessor will classify each joint as swollen yes/no. A score of 0/1 will be given to each swollen joint with 0 representing no swollen and 1 representing a swollen joint. The swollen joint count ranges from 0 to 66 where 0 is considered the best and 66 the worst.

c) Physician's Global Assessments of Disease Activity

Physician's global assessments of the patient's current disease activity will be assessed on an anchored 100 mm horizontal VAS where 0 is considered the best disease activity (no disease activity) and 100 the worst (most disease activity).

d) Patient's Global Assessments of Disease Activity

Patient's global assessments of their current disease activity will be rated on an anchored 100 mm horizontal VAS where 0 is considered the best disease activity (no disease activity) and 100 the worst (most disease activity).

e) Patient's Assessment of Pain

Patients will be requested to indicate their pain intensity due to their RA using a 100 mm horizontal VAS where 0 is considered "No pain" and 100 "the worst pain you can imagine".

f) Patient's Assessment of Physical function – Health Assessment Questionnaire Disease Index (HAQ-DI)

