**D) Change in ACR components over time**

The change in each ACR component will be calculated from baseline of the previous studies.

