### *DAS28-CRP*

When calculating DAS28-CRP, the following rules will be applied in order:

- When calculating the 28TJC and 28SJC, with individual missing joint scores (the “replaced or fused” joints are not taken into consideration for the swelling or tenderness) imputed as the mean of the scored joints, the tender/swollen joint counts after imputation are as follows:

$$28TJC/28SJC = \text{sum (scored tender/swollen joints)} * (\text{number of joints in the full joint set} / \text{number of scored tender/swollen joints})$$

The number of joints in the full joint set is defined as (28 – number of replaced or fused joints) and the scored joints refer to those with an answer (0 – no pain, 1- pain).

- No imputation will be performed.
- If any of the 4 variables: 28TJC, 28SJC, GH (patient global), CRP is missing, then DAS28-CRP will be set to missing.

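### A joint that was active at the original baseline and is replaced or fused later stays in the baseline joint count but leaves the follow-up count, so the SAP formula credits improvement that no other joint shows

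*SAP*

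**What the plan says.** Protocol 8.9: "Joint replacement is permitted during the study". Study drug is interrupted for the operation and restarted after wound healing, with interruption limited to 59 days. A patient who restarts within that limit continues in the observed-case efficacy summaries.

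SAP 2.5.2, on TJC and SJC, separates two kinds of unscored joint. An ordinary missing joint is filled with the mean of the scored joints. A replaced or fused joint is left out altogether, and the set shrinks: "The number of joints in the full joint set is defined as (68 – number of replaced or fused joints) for tenderness". The swollen count uses 66 in the same way. The DAS28-CRP paragraph repeats the rule: "The number of joints in the full joint set is defined as (28 – number of replaced or fused joints"). Appendix C restates it for ACR response, the ACR components and DAS28-CRP.

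The comparator does not move. SAP 2.1.4 says that "the baseline value for efficacy parameters is the original baseline from the previous study databases", and its item D says: "The change in each ACR component will be calculated from baseline of the previous studies". SAP 2.4.5 confirms the original baseline. SAP 2.5.2 sets ACR data to missing after treatment discontinuation; it has no rule for joint surgery.

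**The concern.** The visit count and the baseline count can cover different joints. A joint that was tender and swollen at the original baseline and is replaced in year three contributes to the baseline count but not to any count after the operation. The patient's count falls although no remaining joint has changed, and the formula reads that fall as improvement.

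The measures exposed are TJC, SJC, ACR20/50/70, DAS28-CRP change and EULAR response. DAS28 remission is exposed for a related reason: the joint leaves the absolute score. Long-term efficacy is the secondary objective, reported over 264 weeks or more without a concurrent control, so an artefact of this kind has no comparator to cancel against.

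The SAP does guard against this in its X-ray scoring. In Appendix D, a joint lost to surgery in an adequate segment receives the mean change of the adequately scored joints in that segment, so its loss is not itself counted as improvement. The joint counts have no equivalent. Protocol 9.1.2.7 plans to record joint replacement, but I found no SAP analysis of it.

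**Working it through.** **The plan's own figures.** The tender joints listed in SAP 2.1.4 A(a) sum to 2+2+2+2+2+2+10+2+8+8+2+2+2+2+10+2+8 = 68. For swelling, "The 66 joints to be examined for swelling are the same as those examined for tenderness, except the hip joints are not included", so 68 − 2 = 66. The DAS28 list in item E sums to 2+2+2+10+2+8+2 = 28. All three totals reproduce.

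**What the formula does after a replacement.** With r joints replaced or fused:

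TJC = (sum of scored joints) × (68 − r) / (number scored)

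If every remaining joint is scored, the number scored is 68 − r and the factor is 1. The replaced joints simply drop out.

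**Credited improvement.** Let B be the baseline count. Suppose r of those active joints are later replaced and all others are unchanged. The visit count is B − r and the credited improvement is r/B. The documents give no baseline counts, so B is an assumption shown over a range:

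| B | one joint | two joints |
|---|---|---|
| 5 | 20% | 40% |
| 6 | 16.7% | 33.3% |
| 8 | 12.5% | 25% |
| 10 | 10% | 20% |
| 15 | 6.7% | 13.3% |
| 20 | 5% | 10% |
| 30 | 3.3% | 6.7% |

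With the joint removed from the baseline too, the result is 0% in every cell. Scaling the visit count back up to 68 would not cure it: at B = 10 with one joint replaced, 9 × 68/67 = 9.13, still an 8.7% improvement.

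**A borderline patient.** For ACR20, "a patient must achieve 20% improvement in the Tender joint count (68 joints) and the Swollen joint count (66 joints") and in 3 of 5 other measures. Take a baseline count of 20 and a follow-up count of 17: 3/20 = 15%, not met. If one of those 17 joints, also active at baseline, is replaced, the SAP count is 16: 4/20 = 20%, met. On a common joint set it is (19 − 16)/19 = 15.8%, not met.

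**DAS28-CRP.** The joint terms are 0.56√28TJC + 0.28√28SJC. Dropping one joint that is both tender and swollen gives:

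- 4/3 to 3/2: 0.56(2 − 1.732) + 0.28(1.732 − 1.414) = 0.24
- 10/8 to 9/7: 0.56(3.162 − 3) + 0.28(2.828 − 2.646) = 0.14
- 16/12 to 15/11: 0.56(4 − 3.873) + 0.28(3.464 − 3.317) = 0.11

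**Remission, a deliberately marginal case.** Assume one knee is the only active joint, CRP is 1 mg/L and GH is 40 mm, and read Log as the natural logarithm. DAS28-CRP = 0.56 + 0.28 + 0.36 × ln 2 + 0.56 + 0.96 = 2.61, above the 2.6 cut-off. With the knee replaced it is 0.36 × ln 2 + 0.56 + 0.96 = 1.77, below it.

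**Where no credit arises.** If the replaced joint was inactive at baseline and ten others were active, the count is 10 × 67/67 = 10. No improvement is added, although any later worsening in that joint is hidden. A hip is in the 68-joint tender count only; it is outside both the 66-joint swollen count and the 28-joint list.

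**The case against.** The SAP gives one general formula with no visit qualifier. It does not say that replaced joints are subtracted only at later visits, and a joint already replaced at baseline is left out at both times. This stands: the mismatch follows from a fixed baseline and from silence about later surgery. But a programmer following the text would use the stored baseline and produce it.

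The effect per patient is usually small. One joint reaches the 20% joint threshold alone only when the baseline count is 5 or less, two joints only when it is 10 or less. ACR20 also needs both counts and three other measures, so a hip replacement cannot meet the joint criterion alone. This stands too: the main risk is to borderline classifications.

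Efficacy is secondary, descriptive and uncontrolled, so no test or error rate is affected. That limits the consequence but does not make the change score right.

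Carrying a joint forward as active for the rest of follow-up would create the opposite bias and depart from observed cases. Using carry-forward for the EULAR present score but a common joint set for the change would put two DAS28 values into one classification. Both objections are sound, and the fix below respects them.

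**Conclusion.** The point holds. For a joint active at the original baseline and replaced or fused afterwards, the stated formula and fixed baseline credit r/B improvement with no change elsewhere. For one joint that is 10% at B = 10 and 5% at B = 20, or about 0.24 (at 4/3) and 0.14 (at 10/8) on DAS28-CRP. The direction favours the drug. These figures assume that all remaining joints are scored and unchanged; the baseline counts are illustrative.

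A reader might infer three stronger things that the documents do not support:

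- **Every replacement is a treatment failure scored as benefit.** Protocol 8.9 gives no cause for surgery, and credit arises only if the joint was active at baseline.
- **The share of patients with surgery is the share affected.** Joints inactive at baseline earn no credit, and hips do not enter DAS28 at all.
- **The long-term efficacy results are materially distorted.** The documents give neither a surgery rate nor baseline joint counts, so no group-level effect can be calculated in either direction.

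**What to change.** In SAP 2.5.2 and Appendix C:

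1. Calculate change and percent improvement in TJC and SJC, ACR response, DAS28 change and EULAR response on a common joint set. A joint replaced or fused after the original baseline is removed from that patient's baseline count as well as from the visit count.
2. Use one DAS28 convention for both the change and the present score within each EULAR classification.
3. For DAS28 remission, keep the current rule as the main analysis. Add a sensitivity analysis that carries forward the joint's last score before surgery.
4. Tabulate joint replacements during the study, so that readers can judge how many patients are involved.

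The cost is SAP wording and modest programming. It needs joint-level baseline data from the previous-study databases; the documents do not show whether these are already held with the LTS11210 data. The baseline count will vary by visit for patients who have surgery, which needs a table footnote. Response rates may come out slightly less favourable. If the sponsor already intends a common joint set, items 1 and 2 reduce to a clarifying sentence.
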